## 1. AMENDMENT HISTORY

| Amendment No. | Protocol Version No. | Date issued | Author(s) of changes | Details of Changes made  |
|---------------|----------------------|-------------|----------------------|--|
| 1             | V2.0                 | 08/09/2022  | [name]           | Per recommendation from London-Stanmore REC: The term “Feasibility” removed from all trial documentation, in acknowledgement that this is a full clinical trial. The term “feasibility outcomes” changed to “tertiary outcomes”. |
| 2             | V2.0                 | 08/09/2022  | [name]           | Page 1: REC reference added.   |
| 3             | V2.0                 | 08/09/2022  | [name]           | Section 2: Start date, recruitment end date and trial end date updated to reflect approval dates from REC.   |

Protocol amendments will be listed here whenever a new version of the protocol is produced.

## 2. SYNOPSIS

|                      |   |
|----------------------|---|
| Study Title          | Comparing the effectiveness of computer-aided-design computer-aided-manufacture (CAD/CAM) insoles manufactured from foam-box cast vs direct scan on patient reported outcome measures: A double-blinded, randomised controlled trial  |
| Internal ref. no.    | R&I no GN22OR165  |
| Type of study        | A single centre, double blinded, randomised controlled trial  |
| Trial Design         | Interventional, equivalence Trial design.   |
| Trial Participants   | Participants with a medical condition or lower limb biomechanical deficit which would commonly be treated with the use of insoles, as per the NHS Greater Glasgow and Clyde MSK Foot and Ankle Pathway:
http://www.clinicalknowledgepublisher.scot.nhs.uk/Published/PathwayViewer.aspx?fileId=119  |
| Planned Sample Size  | 114 (57 per group)  |
| Follow-up duration   | Total duration of individual participant involvement: 14-16 weeks total. Including initial assessment and fitting 2-4 weeks, and 12-week follow-up.  |
| Planned Trial Period | Total Project length: 12 Months
Expected Recruitment Start date: 29/09/2022
Expected Recruitment End date: 29/06/2023
Anticipated Trial End Date (all participants completed recruitment, completed intervention, completed all follow up, all data collected and all issues resolved): 29/09/2023   |
| Primary Objective    | To compare the changes in pain in two groups of participants fitted with custom CAD/CAM insoles manufactured using different foot shape capture methods   |
| Secondary Objectives | 

1. To compare the changes in foot function in two groups of participants fitted with custom CAD/CAM insoles manufactured using different foot shape capture methods

2. To compare the changes in foot health in two groups of participants fitted with custom CAD/CAM insoles manufactured using different foot shape capture methods

3. To compare the participant satisfaction in two groups of participants fitted with custom CAD/CAM insoles manufactured using different foot shape capture methods

4. To compare the time-in-transit and cost-time analysis of the custom CAD/CAM insoles manufactured using different foot shape capture methods

5. To compare the environmental impact of custom CAD/CAM insoles manufactured using different foot shape capture methods

 |
| Tertiary Objectives  | 

1. Recruitment rate

2. Participant compliance with the study protocol / Adherence

3. Adverse events

4. Drop-out rate

  |

|  |  |
|--|--|
| Device Type                                | Custom, Computer aided design (CAD) Computer aided manufacture (CAM), Ethylene-vinyl acetate (EVA) Foot Orthoses (insoles)   |
| Manufacturer Name                          | Manufactured in the NHS Greater Glasgow and Clyde Orthotic Department, at Gartnavel General Hospital. Manufactured using the Paromed Paromanager CAD/CAM system  |
| Principle intended use                     | For the use of any persons with a medical condition or lower limb biomechanical deficit which would commonly be treated with the use of insoles, as per the NHS GGC MSK Foot and Ankle Pathway:
http://www.clinicalknowledgepublisher.scot.nhs.uk/Published/PathwayViewer.aspx?fileId=119 |
| Length of time the device has been in use. | These devices are currently used as a standard care across NHS services in the UK, and have been for many years. Both methods of shape-capture are standard clinical practice across the UK. No novel techniques or devices are under investigation within this trial.   |

### 3. ABBREVIATIONS

|          |  |
|----------|--|
| ACRT     | Advanced Clinical Referral Triage  |
| AE       | Adverse event  |
| AR       | Adverse reaction   |
| CAD      | Computer aided design  |
| CAM      | Computer aided manufacture   |
| CI       | Chief Investigator   |
| Co-I     | Co-Investigator  |
| CTA      | Clinical Trials Authorisation  |
| CTRG     | Clinical Trials and Research Governance                                    |
| EVA      | Ethylene-vinyl acetate   |
| FHSQ     | Foot Health Status Questionnaire   |
| GDPR     | General Data Protection Regulation   |
| GGC      | Greater Glasgow and Clyde  |
| GGH      | Gartnavel General Hospital   |
| GRI      | Glasgow Royal Infirmary  |
| MHRA     | Medicines and Healthcare products Regulatory Agency                        |
| MSK      | Musculoskeletal  |
| NHS      | National Health Service  |
| OPUS CSD | Orthotic and Prosthetic User Survey Client Satisfaction with Device Module |
| PI       | Principal Investigator   |
| PIS      | Participant Information Sheet  |
| R&D      | NHS Greater Glasgow and Clyde Research & Development Department            |
| REC      | Research Ethics Committee  |
| RES      | Research Ethics Service  |

|     |                              |
|-----|------------------------------|
| SAE | Serious Adverse Event        |
| SDV | Source Data Verification     |
| SOP | Standard Operating Procedure |

#### **4. BACKGROUND AND RATIONALE**

Computer aided design (CAD) with computer aided manufacture (CAM) foot orthoses (insoles) represent 14% (n=2739, per annum 2020) of all Orthotic Department provision in NHS Greater Glasgow and Clyde (GGC), representing a significant proportion of Orthotic service users, and financial burden to the National Health Service (NHS). The production of CAD/CAM insoles relies on acquiring a digital model of the patient's foot from which the final insole can be produced. This digital model is created either by directly scanning the patient's foot in to the CAD/CAM system to produce a 3D model, or by taking a physical cast of the foot which is then scanned. These two methods of shape-capture are used interchangeably throughout NHS Orthotics services.

In the NHS GGC Musculoskeletal (MSK) Foot and Ankle pathway, patients receive insoles via fully digital design and manufacture, utilising direct foot scanning. Other NHS health-boards and Trusts across the UK have adopted a partially digitised approach, whereby shape-capture is achieved with a traditional foam-box casting method. To date, no work has been undertaken to determine the clinical outcomes and economic impact relating to these different treatment approaches.

Digitisation of medical devices in the orthotics industry conceptualised gains in production speed and reduction in waste materials when compared to traditional manufacture utilising physical shape capture. Yet the continued interim stages of foam cast moulds and physical transportation of casts to manufacturers sacrifices these benefits. As services began adopting CAD systems in place of traditional manufacture, the standard service model for shape-capture has remained in place on some sites, despite the increased accessibility to mobile direct scanners over the past 10 years. In NHS Scotland, the evolution of insole production with the introduction of CADCAM, has therefore lead to the creation of two industry standards; whereby a recent consultation with NHS Health boards across Scotland have shown some services continuing to use traditional foam-box casts, where others have chosen to utilise direct digital scanning on site.

Motivation and hesitation in transitioning to a fully digital work stream have been assumed, but are currently unsupported by research. A common reluctance to adopt direct scanning is based on the assumption that digital shape capture and foam-box casts do not produce like-for-like models, and therefore cannot result in the production of equally effective insoles. Although differences in volume have been shown, the effect on the final device production and ultimately the treatment efficacy and resulting effectiveness have not been evaluated.

Other concerns centralise on costs associated with the acquisition of direct scanning equipment. Although prior cost analyses have shown a fully digital supply chain to be more expensive than a fully traditional supply chain, this does not reflect the practices associated with a partially digital workflow as seen across NHS Scotland. Nor does this consider a cost comparison over the life span of a digital scanner, or the environmental impact of the manufacture and transportation of traditional cast materials.

Overall, the evidence base relating to CAD/CAM insoles, demonstrates little consistency or rationale behind the mode of shape-capture used during the process of manufacture. Often the shape-capture method is undocumented or unclear, or documented without any attributed clinical reasoning. In 2019, Parker et al investigated the differences in a fully digital workflow compared with fully traditional manufacturing techniques, but did not investigate the specific impact of shape-capture in isolation. Furthermore, these studies

report no consideration as to the environmental impact of phenolic foam production and disposal required for traditional foot shape-capture, or the carbon footprint of transportation from manufacturer to digital upload of the foot shape from the foam-box cast, a step which is not required when utilising direct digital scan techniques. In line with NHS Net Zero targets 2020^19, and the recognition of Orthotic Services throughout the UK that largescale change is required to achieve this, the practice of single-use traditional shape capture techniques requires immediate scrutiny.

It is clear from the literature and current widespread indiscriminate practices across NHS Orthotic Services, that more research is required to assist with best practice in the manufacture of CAD/CAM insoles. Given the proportion of Orthotic Service users who receive insoles from the NHS, this trial has the potential to guide practice toward beneficial changes in patient outcomes, as well as providing NHS Orthotic departments with information to assist in the development of long-term service models in line with NHS and Government targets.

## 5. OBJECTIVES AND OUTCOME MEASURES

| Objectives  | Outcome Measures   | Timepoints of evaluation of this outcome measure (as applicable)   |
|---|--|--|
| 
 
Primary Objective
 
 
To compare the changes in pain in two groups of participants fitted with custom CAD/CAM insoles manufactured using different foot shape capture methods
  | 
Foot Health Status Questionnaire (Appendix 1) (FHSQ) – Pain sub-domain. The minimal important difference has a threshold of a 12.5 point change for pain
  | 
Completed at the Second Appointment, Third Appointment, Fourth Appointment and Fifth Appointment
  |
| 
Secondary Objectives
 
 
1. To compare the changes in foot function in two groups of participants fitted with custom CAD/CAM insoles manufactured using different foot shape capture methods
 
2. To compare the changes in foot health in two groups of participants fitted with custom CAD/CAM insoles manufactured using different foot shape capture methods
 
3. To compare the participant satisfaction in two groups of participants fitted with custom CAD/CAM insoles manufactured using different foot shape capture methods
 
4. To compare the time-in-transit and cost-time analysis
 
 | 
 
1. Foot Health Status Questionnaire – Function sub-domain. The minimal important difference has a threshold of a 7.1 point change for foot function
 
2. Foot Health Status Questionnaire – foot health sub-domain. The minimal important difference has a threshold of a -0.4 point change for foot health
 
3. Orthotic and Prosthetic User Survey (OPUS) Satisfaction with device survey (Appendix 2)
 
4. Time-in-transit – Measurement of
 
 | 
 
1. Completed at the Second Appointment, Third Appointment, Fourth Appointment and Fifth appointment
 
2. Completed at the Second Appointment, Third Appointment, Fourth Appointment and Fifth appointment
 
3. Completed at the fifth appointment
 
4. Throughout duration of trial
 
 |

|   |  |  |
|---|--|--|
| of the custom CAD/CAM insoles manufactured using different foot shape capture methods   | transit and delivery times associated with each arm of the trial will be compared.
Cost analysis – Costs relating to time-in-transit for each arm of the trial will be compared   |  |
| 5. To compare the environmental impact of custom CAD/CAM insoles manufactured using different foot shape capture methods                | 5. Analysis of annual custom insole production in NHSGGC in relation to the environmental impact of the required phenolic foam production  and carbon footprint of transportation from manufacturer to digital upload of foam-box cast using carbon foot print calculations  . | 5. Calculated retrospectively from April 2021 – April 2022   |
| Tertiary Objectives

Assessment of factors over a defined 9-month recruitment period including:

1. Recruitment rate | 1. Recruitment rate = $n/\text{recruitment period}$  | 1. Throughout recruitment period and calculated at the trial conclusion                                |
| 2. Participant compliance with the study protocol / Adherence   | 2. Participants will keep a diary of daily wear time, in accordance with prior publications on measuring Orthotic Adherence  . The minimum threshold for adherence is >21 hours per week   | 2. Data collected from participants at the third appointment, fourth appointment and fifth appointment |
| 3. Adverse events   | 3. Adverse events  | 3. Self-reported by participants at any time throughout the trial period                               |
| 4. Drop-out rate  | 4. Dropout rate = $n \text{ dropout}/\text{duration of trial}$   | 4. Collected throughout trial and calculated at trial conclusion                                       |

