#### **6.4.3 Baseline Assessments**

First Appointment – face-to-face visit at the NHS GGC GRI Orthotic clinic, as per standard practice

1. Participant physically attends the clinic
2. Participant is assessed by the PI and Co-I, using the assessment methods outlined above in section 6.4.2
3. Insole specification agreed between the PI, Co-I and participant
4. Participant is assigned a unique participant number.
5. ALL participants receive a direct scan and a foam-box cast, using the methods outlined above in section 9.2
6. PI exits – blinded to the randomisation group
7. Co-I randomises the participant to the treatment arm by opening one of the sealed envelopes: The treatment arm will indicate if the insoles will be manufactured using the direct scan or the foam-box cast.
8. Participant is not informed of the randomisation outcome – blinded to treatment arm
9. Participant is invited to a fitting appointment with the PI in 2-4 weeks and leaves the clinic
10. Co-I creates an insole order on the standard Orthotic department ordering system

11. Co-I sends ALL foam-box casts to Gartnavel General Hospital to be scanned into the CAD/CAM system. The CAD/CAM system records the time and date of each scan, which will be used to inform the time-in-transit aspect of the trial.
12. PI undertakes modelling of both the direct scan and the scanned foam-box cast.
13. Co-I documents the specific functional elements of the insole on the excel data spreadsheet against the unique participant number
14. Co-I documents the assessment findings for each of the biomechanical assessment methods (outlined in section 9.2 of the protocol) on the excel data spreadsheet against the unique participant number

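### Transit time is to be compared by randomised arm, although every participant supplies both a direct scan and a shipped cast

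*Combined protocol and SAP*

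**What the plan says.** Section 5 sets the outcome for secondary objective 4 by trial arm: "transit and delivery times associated with each arm of the trial will be compared". The cost outcome has the same basis: "Costs relating to time-in-transit for each arm of the trial will be compared".

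Section 6.4.3 describes how the data arise:

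- Step 5: "ALL participants receive a direct scan and a foam-box cast".
- Step 7, on allocation: "The treatment arm will indicate if the insoles will be manufactured using the direct scan or the foam-box cast".
- Step 9, the same in both arms: "Participant is invited to a fitting appointment with the PI in 2-4 weeks and leaves the clinic".
- Step 11: "Co-I sends ALL foam-box casts to Gartnavel General Hospital to be scanned into the CAD/CAM system". It continues: "The CAD/CAM system records the time and date of each scan, which will be used to inform the time-in-transit aspect of the trial".
- Step 12: "PI undertakes modelling of both the direct scan and the scanned foam-box cast".

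Section 7.2 adds that direct scans are saved in the CAD/CAM system at the first appointment, that all casts travel by internal mail and are scanned by the technician, and that finished insoles from both arms return by the same courier route.

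No start or stop point is defined for transit or delivery time. Section 9.1 gives statistical methods for the FHSQ and OPUS only.

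**The concern.** The comparison follows the arms, but the quantity of interest does not depend on the arm. A cast is taken, posted and scanned for every participant, whatever the envelope says. The delay that direct scanning would avoid at the capture stage can therefore be observed within each participant, and a between-arm contrast is an indirect way to estimate it.

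The service case for the trial rests partly on this outcome. Section 4 argues that moving casts to the manufacturer gives up the speed gained by digitisation, and it offers the results as a guide to future service models. A small by-arm difference produced by trial logistics could be read as evidence that direct scanning saves no time. An estimate from the foam-box arm's casts alone would be less precise than the data allow.

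**Working it through.** **Inputs from the documents.** The planned size is 114, with 57 per group (sections 2 and 9.2). The 57 reproduces from the plan's own figures: 54/0.95 = 56.8, or 54 × 1.05 = 56.7, and both round up to 57. That calculation is for FHSQ pain; the plan gives no size, SD or precision target for transit. One cast per participant gives 114 planned casts, 57 in each arm.

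**Reading A: cast times come from the foam-box arm only, and direct-scan transit is effectively zero.** The estimate is then the mean cast delay, with 95% CI half-width t(0.975, n−1) × SD / √n.

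- 57 casts: t(0.975, 56)/√57 = 0.265 SD.
- 114 casts: t(0.975, 113)/√114 = 0.186 SD.
- Ratio: 0.186/0.265 = 0.70, so the interval from all casts is about 30% narrower.

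The SD is not given. Under assumed values in days:

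| Assumed SD | Half-width, 57 casts | Half-width, 114 casts |
|---|---|---|
| 0.5 | 0.13 | 0.09 |
| 1 | 0.27 | 0.19 |
| 2 | 0.53 | 0.37 |
| 3 | 0.80 | 0.56 |

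**Reading A when direct-scan times also vary.** Let r be the ratio of scan SD to cast SD, and ρ their correlation within participant. In units of the cast SD:

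- By arm: SE = √[(1 + r²)/57].
- Within participant: SE = √[(1 + r² − 2ρr)/114].
- Example, r = 0.5 and ρ = 0.3: √(1.25/57) = 0.148 and √(0.95/114) = 0.091, a ratio of 0.62.
- Over r from 0 to 1 and ρ from 0 to 0.5 (assumed ranges), the ratio lies between 0.50 and 0.71.

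**Reading B: all 114 cast times are used, tabulated by arm.** No data are lost. But step 11 sends every cast by the same route, and step 7 changes only the file used for manufacture. If casts are handled alike, as described, mean cast transit is the same in both arms and the expected difference is zero. The contrast carries no information about scan against cast.

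**Delivery time by arm.** The arms share the modelling of both files, the return courier and the 2-4 week fitting interval. They differ in the file that is milled. If manufacture in the direct-scan arm waits until the cast has been scanned and both models made, that arm inherits the cast delay and the arm difference tends to zero. If it does not wait, delivery times can differ. Step 12 comes after cast scanning in the list, but nothing says that manufacture waits.

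**The case against.** A reader might infer that the plan throws away half of the cast data. The documents do not say so. Step 11 follows the instruction to send every cast with a statement that scan times will inform time-in-transit, and it sets no limit by arm. The 57 unused times follow from Reading A only.

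A reader might also infer that the two arms share one workflow, so that delivery cannot differ. That is too strong, because the manufactured file differs by arm. A direct scan is in the system at the first appointment, while a cast must first be posted and scanned. The fitting interval limits when insoles are fitted; it does not prevent earlier delivery to the department from being timed.

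Nor do the two harms occur together. Lost precision belongs to Reading A and the null contrast to Reading B.

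Other objections also have force. Without a transit SD, the gain cannot be turned into days or money except by assumption. Section 6.1 lists transit and cost under tertiary outcomes, although sections 2 and 5 make them a secondary objective. The cost concern in section 4 centres on buying scanners and their lifespan cost, which a transit interval does not address. The difference between the two time stamps is not pure transit, since it includes any wait before dispatch and in the scanning queue. Delivery time is a named outcome and should not be dropped.

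These points limit the claim and shape the remedy. They do not show that a by-arm contrast is the better estimate of the capture-stage delay.

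**Conclusion.** The point holds as a modest one. For capture-stage transit, a by-arm contrast either leaves 57 of 114 planned cast times unused or compares casts that were shipped identically. The within-participant difference avoids both problems. Against Reading A it gives a 95% CI about 30% narrower (0.186 against 0.265 SD), assuming direct-scan transit is effectively zero and full recruitment. Under Reading B the gain is one of meaning, not precision: the paired difference compares scan with cast, and the by-arm table does not.

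For delivery time, the possible pull towards no difference is conditional on manufacture waiting for both files, which the documents do not settle.

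One assumption concerns the data. The statement about scan times follows the sentence on casts, so it could mean cast scans only. Direct scans are saved in the same system at the first appointment, so their date at least is known.

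The matter is confined to secondary objective 4 and its cost analysis. The primary outcome is unaffected.

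**What to change.** 1. In section 5, define the capture-to-upload delay as the time stamp of the cast scan at Gartnavel minus the time stamp of the direct scan. State that it includes any wait before dispatch and in the scanning queue.
2. In section 9.1, add a within-participant analysis of this delay in everyone with both captures, reported as a mean (or median) difference with a 95% CI. Base the capture-stage transit cost on it.
3. Keep by-arm delivery time as a reported outcome and define its start and stop points. State whether manufacture in the direct-scan arm waits for the cast to be scanned and modelled, and caveat the interpretation accordingly.

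The cost is protocol wording only. Section 6.4.3 already provides for both captures in everyone and for recording scan times, so no new data collection and no change to sample size are needed.
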